2 PROTOCOL SYNOPSIS

Study Number:	OMP360-01
Title of Study:	An Open-Label Study to Evaluate the Anti-Aging Effects of Three Months of Treatment using the Obagi 360 System in Subjects with Photodamage
Study Center(s):	Up to two study centers in the United States
Study Period:	3Q13 – 2Q14
Objectives:	To observe improvement in the appearance and the effects of the Obagi 360 skincare system when used consistently over a 3 month time period

Methodology: Open-label study of the Obagi 360 system used daily for 3 months to evaluate the effects on photodamage. Subjects will be evaluated at five time points; a baseline visit and at 2, 4, 8, and 12 weeks. The total study duration will be 12 weeks for each subject.

At the baseline visit (Day 1) the subject will complete the informed consent and photo release and will be evaluated for eligibility. Eligible subjects will be assigned a subject number and enrolled. At the baseline visit photographs will be taken and the investigator will complete the skin grading assessment. The subject will be instructed in the use of the product. The Obagi 360 skincare system will be applied once daily.

The subjects will return to clinic on Days 14 (\pm 2 days), and 28, 56, and 84 (\pm 5 days) to assess response. At each visit photographs will be obtained and the investigator will complete the skin grading assessment. Additionally, the subject will complete a self-assessment at subsequent visits.

Number of Subjects: A total of approximately 40 subjects will be enrolled

Inclusion Criteria: Subjects may participate in the study if they meet the following criteria:

- 1. Female subjects between the ages of 25-40
- 2. Fitzpatrick skin type I-IV
- 3. Investigator Assessment of Overall Integrated Facial Photodamage of mild to moderate (score of 2 5 inclusive; Section 11.1) and prone to breakouts (non-inflammatory), as assessed by the investigator.
- 4. Willing to withhold use of all other topical skincare products during the study with the exclusion of facial cleansers and Latisse. Make-up is allowed.
- 5. Willing to withhold all facial treatments during the course of the study including toxins, fillers, microdermabrasion, IPL, peels, facials, laser treatments, tightening treatments. Waxing and threading is allowed but not facial laser hair removal.
- 6. Willing to remove all makeup at every visit for pictures.
- 7. Willing to sign Photo release.
- 8. Willing and able to give written informed consent.

- 9. Subject is able to follow study instructions, accessible for treatment and follow-up at the specified time on the specific required study visit days, and likely to complete all study requirements
- 10. Female subjects of child bearing potential agree to take a urine pregnancy test at the Baseline visit, end of the study and when deemed appropriate by Investigator and/or Sponsor. Subjects of childbearing potential is defined as any female who has experienced menarche and who:
 - a. Has not undergone successful surgical sterilization (i.e. hysterectomy or bilateral oophorectomy)

Or

b. Is not post-menopausal (i.e. amenorrhea equal to or greater than 12 consecutive months)

Or

- c. Is on hormone replacement treatment (HRT) with a documented serum follicle stimulating hormone (FSH) level of >35mIU/mL
- 11. Be using an acceptable method of contraception throughout the study if they are female of child-bearing potential. Acceptable methods of birth control include: oral and other systemic contraceptives, double barrier, bilateral tubal ligation, partner vasectomy and abstinence. Oral and other systemic contraceptives must be stable for three months prior to the Baseline visit. Patients on oral contraceptives agree not to alter their oral contraceptive, including dose or regimen for the duration of the study
- 12. No clinically significant abnormal findings based on the medical history including medication history that may affect study participation as determined by the Investigator
- 13. No recent history of drug or alcohol abuse.

Exclusion criteria: Subjects will be excluded from the study if they meet any of the following criteria:

- 1. Have known hypersensitivity to any components of the Obagi 360 products
- 2. Currently taking oral retinoids
- 3. Use of any of the following in the preceding 6 months: any laser or IPL treatment, toxin, chemical peel, dermabrasion
- 4. Use of any product which may cause irritation as per the judgment of the investigator
- 5. Use of topical retinoids in the preceding 3 months
- 6. Use of Alpha or Beta hydroxy acids in the preceding month
- 7. Significant history of eczema, atopic dermatitis, psoriasis in the facial area
- 8. Any active facial inflammatory condition.
- 9. Female subject that is pregnant, breast feeding, or planning a pregnancy during the course of the study

- 10. History of poor cooperation, non-compliance or unreliability
- 11. The Investigator deems the subject an unsuitable candidate for this study

Test product, dose and mode of administration:

Obagi 360 System consisting of: Obagi 0.5% retinol, Hydrafactor SPF30, and Exfoliating cleanser. The system will be used once daily for 3 months.

Reference therapy, dose and mode of administration:

None

Duration of treatment, enrollment and follow-up:

Duration of treatment period: 12 weeks

Criteria for evaluation:

- 1. Improvement in manifestations of photodamage assessed by the investigator using the Investigator's Skin Grading Assessment.
- 2. Assessment of improvement by the subject using the Subject's Self-Assessment.

Safety:

Safety variables include treatment-emergent adverse events (AEs), serious AEs (SAEs), treatment related AEs, and AEs leading to study discontinuation.

The investigator will assess the tolerability of the product at each visit.

Sample size:

Forty subjects will be enrolled. Forty (40) subjects are adequate to obtain information on the anti-aging effects of the Obagi 360 system.

Statistical methods:

The effect of the Obagi 360 system on photodamage will be evaluated using the Investigator's Skin Grading System. The changes from baseline in the scores will be summarized and tested for significance using the paired T-test for each time point. In addition, a summary of the distribution or scores (improvement or worsening) will be summarized and categorized as the number and proportion of subjects "Improved", "Equal to" or "Worse" than baseline.

For the Subject's Self-Assessment, the response to each question will be summarized by the proportion of subjects in each category. No statistical testing will be performed on the Subject's Self-Assessment.

Safety will be summarized by the incidence of adverse events over the study by body system and preferred term. The tolerability will be summarized by the proportion of subjects with none, mild, moderate, and severe for each assessment by visit.

5 ETHICS

5.1 INSTITUTIONAL REVIEW BOARD (IRB)

The principal investigator will provide the IRB with all appropriate materials to permit their review and approval of the protocol. No study subject will be admitted to this study until written IRB approval of the protocol and the informed consent template has been obtained by the investigator. The investigator should file all related correspondence with the IRB. Copies of IRB approvals will be forwarded to Obagi or designee. The product for this study will not be delivered to the study site until copies of IRB approvals for the site have been supplied by the investigator to Obagi or designee.

Appropriate reports on the progress and conclusion of this study by the principal investigator must be made to the IRB at least annually in accordance with applicable government regulations. The investigator is responsible for checking what additional local reporting procedures may be applicable and complying with these requirements. Federal regulations also provide for expedited reporting of certain events to the IRB (see Section 14.2). The investigator is responsible for expedited reporting requirements that may be imposed by his or her IRB.

5.2 ETHICAL CONDUCT OF THE STUDY

The study will be performed in accordance with the recommendations guiding physicians in biomedical research involving human subjects adopted by the 18th World Medical Assembly, Helsinki, Finland, 1964, and later revisions (insofar as such revisions are consistent with United States [US] treaty obligations and in accordance with US law), with the Common Rule (Part 46 of Title 45 of the US Code of Federal Regulations) and with Parts 50 and 56 of Title 21 of the US Code of Federal Regulations.

5.3 STUDY SUBJECT INFORMED CONSENT

The informed consent process is intended to give a study subject or patient or his or her designated representative all the information (s)he would reasonably want to know about a study, to ensure that the study subject understands the information and to give the study subject an opportunity to agree to participate in the study. A properly executed written informed consent, which has been approved by an IRB and is in compliance with 21 CFR Part 50, shall be obtained from each study subject before any study-specific procedures have been performed. The subjects must be informed about their right to withdraw from the study at any time, and that withdrawal will not affect their future medical care, treatment or benefits to which the subject is otherwise entitled. The study subject should also be informed if privacy rights under this study are exempt from the confidentiality provisions of the Health Insurance Portability and Accountability Act of 1996 pursuant to 45 CFR § 512(b)(iii) and, if so, what components of study subject confidentiality will be maintained and by whom.

CONFIDENTIAL AND PROPRIETARY INFORMATION OF OMP, INC.

The investigator shall provide a copy of the signed and dated informed consent to the study subject and will keep the original, signed form in the study subject's study file. The investigator will confirm the receipt of informed consent from each subject by a recording in the case report form (CRF).

6 BACKGROUND AND RATIONALE

6.1 BACKGROUND

Obagi products are the #1 prescription-strength, physician-dispensed skin care system in the world. The Obagi 360 System is a complete skin rejuvenation system and works on three different levels to make sure that skin gets the ultimate care, from treating skin problems to pampering the skin, and making sure that the body's largest organ functions at its best.

Obagi 360 contains: Obagi Exfoliating Cleanser, Obagi 0.5% retinol, and Hydrafactor Broad Spectrum SPF30. When used together under the guidance of a dermatologist/physician, these products are anticipated to work synergistically to provide improvement in the appearance in photodamage, fine lines, and wrinkles.

Subjects will use the Exfoliating Cleanser in the morning and evening. After use of the Exfoliating Cleanser in the morning, the Moisturizing Cream will be applied, and after use of the Exfoliating Cleanser in the evening, the Night Cream will be applied. The Exfoliating Cleanser is composed of maltodextrin (and) Eperua Falcata Bark Extract and is intended to gently exfoliate the skin in preparation for the moisturizing retinol cream. The 0.5% retinol (in both the Moisturizer and the Night Cream) is intended to improve skin texture and evens out roughness. For protection, the Hydrafactor SPF30, a physical sunblock, is used as part of the Moisturizer.

6.2 RATIONALE

The Obagi 360 System is intended for daily application. This study is designed to evaluate the effects on anti-aging when the Obagi 360 system is used daily for up to 3 months.

7 STUDY OBJECTIVE

To observe improvement in the appearance and the effects of the Obagi 360 skincare system when used consistently over a 3 month time period.

7.1 STUDY DESIGN OVERVIEW

This is an open-label study of the Obagi 360 system used daily for 3 months to evaluate the effects on photodamage. Subjects will be evaluated at five time points; a baseline visit and at 2, 4, 8, and 12 weeks. The total study duration will be 12 weeks for each subject.

At the baseline visit (Day 0) the subject will complete the informed consent and photo release and will be evaluated for eligibility. Eligible subjects will be assigned a subject number and enrolled. At the baseline visit photographs will be taken and the investigator will complete the skin grading assessment. The subject will be instructed in the use of the product. The subjects will return to clinic on Days 14, 28, 56, and 84 (\pm 5 days) to assess response. At each visit photographs will be obtained and the investigator will complete the skin grading assessment. Additionally, the subject will complete a self-assessment at subsequent visits.

7.2 STUDY SUBJECT ASSIGNMENT, RANDOMIZATION, AND BLINDING

This study is being conducted open-label. There is no blinding of the investigator or subject. Enrolled subjects will be assigned a sequential number at each site.

Study center(s) will be instructed to enroll approximately 30% of subjects who are prone to mild breakout (non-inflammatory).

7.3 SCHEDULE OF STUDY PROCEDURES

A table outlining the schedule of procedures for this study is presented in Table 1.

Table 1 Procedures Flow Chart

PROCEDURES	BASELINE (DAY 0)	DAY 14 (± 2 Days) and DAY, 28, 56, and 84 (± 5 Days)
	Visit 1	Visits 2 through 5
Obtain Informed Consent, HIPAA Authorization	X	
Obtain Photographic Release Form	X	
Review Inclusion/Exclusion Criteria	X	
Review Medical History	X	
Obtain Subject Demographics	X	
Conduct Investigator's Skin Grading Assessment	X	X
Urine Pregnancy Test ¹	X	X
Obtain Photographs	X	X
Conduct Subject's Self-Assessment ²		X
Assign Subject Number	X	
Review Obagi 360 Application ³	X	X
Dispense/Collect Obagi 360 System	X	X
Assess Tolerability		X
Review Concomitant Medications	X	X
Review Adverse Events		X
Review Compliance with Study Procedures		X

UPT obtained on subjects of child bearing potential only.

7.4 DURATION OF SUBJECT PARTICIPATION

The duration of the treatment is daily for 12 weeks. Subjects will be expected to come to the study center for the baseline visit and 4 additional study visits.

Subject's Self-Assessment of improvement Questionnaire (Appendix 2) will only be administered at Visit 2 and Visit 3

Subjects receive instruction during visit on how to apply study treatment product. The first application of study treatment product to the face will be applied at the conclusion of the Baseline visit as part of the Study Treatment Dispensing and Application Training.

8 SELECTION OF STUDY POPULATION

8.1 INCLUSION CRITERIA

Individuals eligible for inclusion in this study must meet all the following criteria:

- 1. Female subjects between the ages of 25-40
- 2. Fitzpatrick skin type I-IV
- 3. Investigator Assessment of Overall Integrated Facial Photodamage of mild to moderate (score of 2 5 inclusive; Section 11.1) and prone to breakouts (non-inflammatory), as assessed by the investigator.
- 4. Willing to withhold use of all other topical skincare products during the study with the exclusion of facial cleansers and Latisse. Make-up is allowed.
- 5. Willing to withhold all facial treatments during the course of the study including toxins, fillers, microdermabrasion, IPL, peels, facials, laser treatments, tightening treatments. Waxing and threading is allowed but not facial laser hair removal.
- 6. Willing to remove all makeup at every visit for pictures.
- 7. Willing to sign Photo release.
- 8. Willing and able to give written informed consent.
- 9. Subject is able to follow study instructions, accessible for treatment and follow-up at the specified time on the specific required study visit days, and likely to complete all study requirements
- 10. Female subjects of child bearing potential agree to take a urine pregnancy test at the Baseline visit, end of the study and when deemed appropriate by Investigator and/or Sponsor. Subjects of childbearing potential is defined as any female who has experienced menarche and who:
 - a. Has not undergone successful surgical sterilization (i.e. hysterectomy or bilateral oophorectomy)

Or

b. Is not post-menopausal (i.e. amenorrhea equal to or greater than 12 consecutive months)

Or

c. Is on hormone replacement treatment (HRT) with a documented serum follicle stimulating hormone (FSH) level of >35mIU/mL

- 11. Be using an acceptable method of contraception throughout the study if they are female of child-bearing potential. Acceptable methods of birth control include: oral and other systemic contraceptives, double barrier, bilateral tubal ligation, partner vasectomy and abstinence. Oral and other systemic contraceptives must be stable for three months prior to the Baseline visit. Patients on oral contraceptives agree not to alter their oral contraceptive, including dose or regimen for the duration of the study
- 12. No clinically significant abnormal findings based on the medical history including medication history that may affect study participation as determined by the Investigator
- 13. No recent history of drug or alcohol abuse

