11 ASSESSMENT OF EFFECTS

11.1 INVESTIGATOR'S SKIN GRADING OF PHOTODAMAGE

At the baseline visit the investigator will assess the facial skin for photodamage based on the grading scale below. The grading scale is a static scale. At each subsequent visit, the investigator will assess the facial skin for effects of treatment with the Obagi 360 system using the same scale. No reference to grading at prior visits will be made. Assessment of the components of photodamage will be made on a 7-point scale as shown below.

Investigator's Skin Grading Scale Manifestations of Facial Photodamage

Overall Rating Scale: 0= None, 1= Minimal, 2-3 = Mild, 4-5= Moderate, 6= Severe

Fine Wrinkling Number and depth of superficial wrinkles, fine lines typically

appearing in periorbital and perioral regions,

Mottled Assessment of light patchy mottled hyperpigmentation and solar

Hyperpigmentation freckling based on qualitative criteria such as area/density of

pigment, color intensity, uniformity of distribution

Sallowness Visual assessment of color tone from pink or rosy to very sallow or

pale- The opposite of radiance

Loss of texture Visual assessment of surface properties of the skin, i.e., skin grain

and smoothness

Pore visibility Appearance of pores, especially on the nose and cheek areas

Breakouts Small non-inflammatory acneic lesions

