11.1.1 INVESTIGATOR FACIAL PHOTODAMAGE CHARACTERISTICS ASSESSMENT

Efficacy evaluations for each of the following dermatological characteristics will be conducted according to Table 2: fine wrinkling, mottled hyperpigmentation, sallowness, loss of texture, pore visibility, and breakouts.

Table 2 Investigator's Skin Grading Scale

Invest	Investigator Assessment of Manifestations of Facial Photodamage								
	FAC	IAL PHOTO	DAMAGE S	SKIN GRA	ADING SC	ORE			
Severity	FINE WRINKLING (circle one)	MOTTLED HYPER- PIGMENTATION (circle one)	SALLOWNESS (circle one)	LOSS OF TEXTURE (circle one)	PORE VISIBILITY (circle one)	BREAKOUTS (circle one)			
None	0	0	0	0	0	0			
Minimal	1	1	1	1	1	1			
Mild	2	2	2	2	2	2			
Mild	3	3	3	3	3	3			
Moderate	4	4	4	4	4	4			
Moderate	5	5	5	5	5	5			
Severe	6	6	6	6	6	6			

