14.2.3 ANALYSIS OF IMPROVEMENT IN PHOTODAMAGE BY INVESTIGATOR

For each of the components of the Investigator's Skin Grading Assessment for improvement in photodamage, the data will be summarized in the format shown in Table 4.

In the case of the Investigator's Assessments asked at each timepoint, a Paired T-Test will be used to compare the individual scores at each time point relative to their respective baselines for each treatment cell. The net change scores for each attribute will be shown as a distribution and converted to the number of subjects who showed "improvement", "stayed the same" or "worsened".

For all analyses unless otherwise specified, a two tailed p < 0.05 will be taken as the level of significance.

Table 4 Format for Summary of Investigator's Skin Grading Scale

Investigator's Skin Grading Skin Grading Component (e.g., Sallowness)

	Mean ± S.D.	P-value					
Baseline							
Day 14							
Day 28							
Day 56							
Day 84							
Net Change from Baseline							

Day 14	
Day 28	
Day 56	
Day 84	

Distribution of (Net Change) Scores

	-4	-3	-2	-1	0	+1	+2	+3	+4
Day 14									
Day 28									
Day 56									
Day 84									
	Two		d				7	X/orac	^

	ımprovea	=	vvorse
Day 14			
Day 28			
Day 56			
Day 84			

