14.3 SAMPLE SIZE

Forty subjects will be enrolled. Forty subjects are adequate to obtain information on the antiaging effects of the Obagi 360 system.

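### Inclusion criterion 3 makes every subject breakout-prone while Section 7.2 sets a target of about 30%, so the breakout mix of the study population is ambiguous

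*Protocol*

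**What the plan says.** Section 8.1 of the Protocol introduces its list with "Individuals eligible for inclusion in this study must meet all the following criteria". Criterion 3 has two parts joined by a plain conjunction: an overall integrated photodamage score of 2 to 5, "and prone to breakouts (non-inflammatory), as assessed by the investigator". The synopsis carries the same criterion.

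Section 7.2 adds a recruitment instruction: "Study center(s) will be instructed to enroll approximately 30% of subjects who are prone to mild breakout (non-inflammatory" (the closing bracket follows). Section 8.3 allows up to two centers and stops enrolment at 40. On sample size, Section 14.3 says only: "Forty subjects will be enrolled. Forty subjects are adequate to obtain information on the antiaging effects of the Obagi 360 system".

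Breakouts is also an outcome. Section 11.1.1 grades "fine wrinkling, mottled hyperpigmentation, sallowness, loss of texture, pore visibility, and breakouts", and Section 11.1 describes the last of these as "Small non-inflammatory acneic lesions", scored 0 to 6 at baseline and at each later visit. Under Section 14.2.3, "a Paired T-Test will be used to compare the individual scores at each time point relative to their respective baselines", and subjects are also counted as improved, unchanged or worse. Section 14.1 uses all available data for this and names no breakout-prone subset. Appendix 3 (Part 2) has two items on breakouts, one on visibility and one on frequency.

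**The concern.** A target of about 30% makes sense only if subjects who are not breakout-prone may enter. Criterion 3 does not let them in. A center that follows Section 7.2 would enrol subjects who fail an inclusion criterion. A center that follows Section 8.1 cannot come near the target. With up to two centers, each could settle the matter differently, and site would then be confounded with breakout status.

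The effect on the results is specific. A subject who scores 0 on Breakouts at baseline can only stay the same or worsen. The more such subjects are enrolled, the smaller the mean improvement and the larger the unchanged group, whatever the product does. The two breakout items in the self-assessment depend on the mix in the same way. For the other photodamage components, the question is whether the findings describe photodamaged women in general or only those who also break out.

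A statistical analysis plan cannot repair this. Eligibility and recruitment instructions belong to the protocol and take effect before any analysis.

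**Working it through.** **Head count.** Inputs: N = 40 (Sections 8.3 and 14.3), the rule that all criteria apply (Section 8.1), and the target of about 30% (Section 7.2).

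- Criterion 3: 1.00 × 40 = 40 breakout-prone subjects.
- Section 7.2, plain reading: 0.30 × 40 = 12 prone subjects, leaving 40 − 12 = 28 who are not.

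The two counts cannot both hold, and no section reconciles them.

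**The plan's own figure.** N = 40 comes with no power, effect size or SD, so there is no calculation to reproduce.

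**Illustration of what the mix does to Breakouts.** The test is the planned paired t-test on all 40 subjects, under the stated rule that "For all analyses unless otherwise specified, a two tailed p < 0.05 will be taken as the level of significance". The effect sizes are assumptions. Prone subjects improve by m points with SD s. The others have zero change with no variance. With prone share p:

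- mean change in all subjects = p·m
- variance = p·(s² + m²) − (p·m)²
- standardised change d = mean / SD
- power from the noncentral t with 39 degrees of freedom and noncentrality d·√40

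For m = 0.5, s = 1.0, p = 0.30: mean = 0.15; variance = 0.30 × 1.25 − 0.0225 = 0.3525; SD = 0.594; d = 0.253; power about 34%. With p = 1: d = 0.50; power about 87%.

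| Assumed change in prone subjects | Mean / SD, 30% mix | d, 30% mix | Power, 30% mix | Power, all prone |
|---|---|---|---|---|
| 0.5 (SD 1.0) | 0.15 / 0.594 | 0.253 | 34% | 87% |
| 1.0 (SD 1.5) | 0.30 / 0.941 | 0.319 | 50% | 98% |
| 1.0 (SD 1.0) | 0.30 / 0.714 | 0.420 | 74% | >99% |

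In every row the expected mean change under the 30% mix is 30% of its value in prone subjects. That ratio follows directly from the zero-change assumption.

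**The case against.** The strongest reply is that the two sections speak of different things. Criterion 3 mentions breakouts without a severity, while Section 7.2 mentions mild breakout. One could therefore read that all subjects are prone and about 30% of them mildly so. The protocol even has a scale for this: Breakouts is graded at baseline, and scores 2 and 3 are labelled mild. The reading is possible, but no section states it. The scale grades lesions present on the day, whereas both rules speak of proneness. No entry threshold on the scale is set, and nothing says what the other 70% or so should be. It is one of the ways the sponsor might resolve the conflict, but it does not remove it.

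A second reply is that the stakes are modest. The study is open-label and aims to observe improvement. No primary endpoint is named, Breakouts is one of six components beside an overall score, and the self-assessment is not tested. The baseline Breakouts scores would let the lesion mix actually recruited be described afterwards. All of that stands, and it limits the damage to the breakout results and to generalisability. It does not tell a site whom to enrol.

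Some stronger inferences are tempting but lack support:

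- **That the Breakouts endpoint or the whole population is undefined.** Its description, scale, visits, test and analysis set are all stated. So are sex, age, skin type and the photodamage range.
- **That Breakouts rests on 12 subjects.** With n = 12 the detectable change at 80% power would be 0.89 SD, against 0.45 SD with n = 40. The protocol plans no such subset analysis, so the effect to consider is dilution across all subjects.
- **That only prone subjects can show a change.** Nothing says that the others score 0 at baseline. Anyone scoring 1 or more can improve, and anyone below 6 can worsen.

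**Conclusion.** The contradiction holds. On a plain reading, criterion 3 gives 40 of 40 breakout-prone subjects and Section 7.2 about 12 of 40, and following one instruction breaches the other. The conclusion rests on the text alone.

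The power figures are only an illustration. They rest on assumed effects and on no change at all in subjects who are not prone. Improvement in some of those subjects would narrow the gap. Random variation in their scores would lower the mixed-population power further.

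A reader might infer that Section 7.2 shows the true intent and that about 28 enrolled subjects would be eligibility violations. The 28 follows from one interpretation of an approximate target that carries no stated cap, and nothing in the protocol shows which section expresses the intent. What is established is that the breakout mix is ambiguous, and with it the meaning of the Breakouts results and of the two related self-assessment items. The photodamage entry range and the definition of the Breakouts score are unaffected.

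**What to change.** The sponsor should state which population is intended and reconcile the sections before the first subject is screened, in one of two ways:

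1. Remove the breakout condition from criterion 3 in both the synopsis and Section 8.1. Keep the target of about 30% in Section 7.2, say whether it applies per center or overall, and record breakout-proneness for each subject at baseline.
2. Keep criterion 3, and either delete the 30% instruction or reword it in terms of the baseline Breakouts score, so that sites can apply it.

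Either way the cost is a short amendment with the approvals that Section 15.7 requires. The first option also needs one baseline item, if the case report form (not shown) does not already have it. Neither needs extra subjects or visits.
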